9.8 Recurrence of Disease

Recurrent malignancy will be defined by hematologic criteria. Recurrent malignancy will also be defined as any unplanned medical intervention designed to prevent progression of malignant disease in patients who have molecular, cytogenetic, or flow cytometric evidence of malignant cells after transplantation.

9.9 Overall Survival (OS)

Overall survival is defined as the time from the first date of treatment until death as a result of any cause. For OS time, patients that have not died or are lost to follow-up will be censored at the date the patient was last known to be alive or the date of last contact.

CONFIDENTIAL

9.10 Time to Absolute Neutrophil Count (ANC) and Platelet Count Recovery

Time to neutrophil recovery is defined as the time from each CPX-351 cycle Day 1 to when the peripheral ANC is $\geq 500/\mu\text{L}$. Time to platelet recovery is defined as the time from each CPX-351 cycle to when the peripheral blood platelet count is $> 50,000/\mu\text{L}$. Delayed neutrophil recovery is defined as having an ANC $< 500/\mu\text{L}$ > 56 days from each CPX-351 cycle Day 1. Delayed platelet recovery is defined as having a platelet count $< 50,000$ > 56 days from each CPX-351 cycle Day 1.

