Study Drug, Dose, and Mode of Administration:	
Induction phase: CPX-351 (daunorubicin 44 mg/m² IV and cytarabine 100 mg/m² IV) will be given on Days 1, 3, and 5 followed by 30 mg quizartinib by mouth (PO) once daily on Days 8-21. Patients with an incomplete response, but a >50% reduction in the blast count/cellularity ratio compared to the most recent bone marrow (BM) biopsy prior to treatment, should receive one additional cycle of induction therapy (re-induction) with CPX-351 (daunorubicin 44 mg/m² IV and cytarabine 100 mg/m² IV) on Days 1 and 3 only. Re-induction will begin after a 72-hour washout period from the last dose of quizartinib. During re-induction, treatment with quizartinib will resume on Day 6 and continue through Day 21. Any patient with neutropenia or thrombocytopenia lasting ≥ 56 days from the initiation of CPX-351 will not receive consolidation and will instead proceed to the maintenance phase.
 
Consolidation phase: At the Investigator's discretion, patients who achieve CR and do not proceed to an alloHCT or other CT intervention will proceed to the consolidation phase beginning 7 days (± 7) after neutrophil recovery (ANC >1000/μL). Administer up to 2 consolidation cycles of CPX-351 (daunorubicin 29 mg/m² IV and cytarabine 65 mg/m² IV) on Days 1 and 3. Begin quizartinib 30 mg PO once daily on Days 6-21.
 
Maintenance phase: Maintenance dosing of quizartinib will begin at 30 mg/day on Days 1-14, and if there are no non-hematologic Grade ≥ 3 toxicities, the quizartinib dose will increase to 60 mg/day on Day 15. The maintenance phase is a 28-day cycle beginning 7 days (± 7) after neutrophil recovery (ANC >1000/μL) from the consolidation phase or induction phase. Patients will receive quizartinib once daily for a total of 24 cycles or until disease relapse

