5.2.1.2 Outpatient procedures

Consolidation cycles may be administered on an outpatient basis with IV infusion of CPX-351 and three weekly lab checks (Monday, Wednesday, and Friday) and weekly provider visits. Maintenance cycles are all outpatient with monthly lab/provider visits.

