5.2.3 Consolidation Phase

Patients who achieve a CR and do not proceed to an alloHCT or other CT intervention will proceed from induction to the consolidation phase beginning 7 days (± 7 days) after neutrophil recovery (ANC $> 1000/\mu\text{L}$), receiving up to 2 consolidation cycles consisting of CPX-351 (daunorubicin 29 mg/m² IV and cytarabine 65 mg/m² IV) on Days 1 and 3. Quizartinib therapy (30 mg PO once daily) will start on Day 6 and continue through Day 21.

After the first consolidation cycle, if it is believed by the PI and/or sub-investigator that a patient with prolonged Grade ≥ 3 toxicity would have additional adverse toxicities during the second consolidation phase, and/or there is CRi with persistent ANC $< 1000/\mu\text{L}$ and/or platelets $< 50,000/\mu\text{L}$ more than 14 days from the recovery marrow assessment, then the patient could proceed to a cellular intervention or the maintenance phase.

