6. STUDY ASSESSMENTS AND EVALUATIONS

6.1 Overview

All patients should visit the study center on the days specified within this protocol. The complete Schedule of Assessments for this study is presented in Appendix D.

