6.4.2 Consolidation Phase (If applicable)

- Patients who achieve CR and do not receive an alloHCT or other CT intervention will receive up to 2 cycles of consolidation therapy with CPX-351 and quizartinib.
- Serum pregnancy test once per cycle during the consolidation phase

6.4.2.1 Cycle 1, Day 1 and 3

- Physical examination and vital signs
- ECOG performance status
- AE monitoring
- Concomitant medication review
- CBC and clinical chemistry panel
- CPX-351 (Days 1 and 3)
- ECG (Day 3)

6.4.2.2 Cycle 1, Day 6

- Physical examination and vital signs
- ECOG performance status
- AE monitoring
- Concomitant medication review
- CBC and clinical chemistry panel
- ECG and QTcF assessment (if QTcF \leq 470 msec, resume quizartinib on Day 4)
- Quizartinib (begin daily until Day 21)

6.4.2.3 Cycle 1 Days 14 and 21

- ECG

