10.4 Data Analysis

Descriptive statistics, including mean, median, standard deviations, and ranges for all continuous measures, will be tabulated and reported. Percentages and frequencies for all categorical measures will also be presented. Time-to-event endpoints will be reported using Kaplan-Meier estimates, with 95% CIs for median time to event.

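### Neutrophil recovery in Section 9.10 needs no prior fall in ANC, so it is normally met on Day 1 of consolidation cycle 1; platelet transfusion and death before recovery have no rule

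*Combined protocol and SAP*

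**What the plan says.** Section 9.10 defines the neutrophil endpoint: "Time to neutrophil recovery is defined as the time from each CPX-351 cycle Day 1 to when the peripheral ANC is" at least 500/µL. For platelets it says: "Time to platelet recovery is defined as the time from each CPX-351 cycle to when the peripheral blood platelet count is" above 50,000/µL. Neither definition asks for an earlier value below the threshold, a sustained value or a transfusion-free interval. Neither says what happens to a patient who dies, starts other therapy or never recovers.

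Section 5.2.3 governs entry to consolidation. A patient in CR who is not going to transplant or other cellular therapy "will proceed from induction to the consolidation phase beginning 7 days" (±7 days) after neutrophil recovery, there defined as ANC >1000/µL. The synopsis says the same.

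Section 10.4 gives the analysis: "Time-to-event endpoints will be reported using Kaplan-Meier estimates, with 95% CIs for median time to event". Section 2.3.2 lists the endpoint with a platelet threshold of ≥50,000/µL.

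On blood counts, Section 6.1 says: "The complete Schedule of Assessments for this study is presented in Appendix D". Section 6.5.6 also sends CBC timing to Appendix D. Section 5.2.1.2 adds: "Consolidation cycles may be administered on an outpatient basis with IV infusion of CPX-351 and three weekly lab checks" on Monday, Wednesday and Friday. Section 5.2.1.1 gives the same frequency to induction patients discharged after a clear Day 21 marrow.

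**The concern.** Section 1.5 names pancytopenia as the most anticipated side effect. It raises the possibility that quizartinib protects normal progenitors, and says this will be judged by comparing the timing of count recovery with earlier CPX-351 studies. Section 7.5.2 quotes earlier rates of prolonged cytopenia in consolidation (neutrophils 10%, platelets 25%, both beyond Day 42). This endpoint therefore carries the evidence on how long the combination suppresses the marrow.

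A recovery time that stops at the first qualifying value, with no nadir required, does not measure recovery in a patient who starts the cycle with adequate counts. A platelet count raised by transfusion is not marrow recovery. Censoring a death treats the patient as someone who would have recovered later at the same rate as the survivors. The last two defects make recovery look quicker or more complete than it was, and the first yields zeros.

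**Working it through.** The plan gives no sample size, estimate or target for this endpoint, so there is no stated figure to reproduce. The check is of definitions, followed by arithmetic on assumed inputs.

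**1. Day 1 of consolidation cycle 1**
- Start condition (5.2.3): ANC >1000/µL reached, then 7 ± 7 days, that is 0 to 14 days later.
- Stop condition (9.10): ANC ≥500/µL, clock starting on cycle Day 1.
- Because 1000 > 500, the stop condition already holds on Day 1 unless the ANC has fallen below 500 in those 0 to 14 days. Time = 0 days.

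If cycles were pooled, with one induction per patient, one consolidation cycle per responder and all of those scored 0 (assumptions), the share of zeros would be r/(1 + r) for response rate r:
- r = 0.27 (the null rate in 10.2): 0.27/1.27 = 21%
- r = 0.50 (the alternative in 10.2): 0.50/1.50 = 33%

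**2. Platelets**
- 2.3.2 uses ≥50,000. Section 9.10 uses >50,000 for recovery and <50,000 for delayed recovery, so a count of exactly 50,000 is neither under 9.10.
- No transfusion condition appears in either place. The documents give no transfusion rate, so the size of this effect cannot be computed.

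**3. Death before recovery**

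Sections 9.5, 9.7 and 9.9 state censoring rules for DOR, EFS and OS. Section 9.10 states none. Illustration, all inputs assumed: recovery time Normal(34, 7) days, clipped to 18–56; a proportion d dies before recovery, uniformly over Days 8–45; 15% of the others have not recovered by Day 56. The true proportion recovered is (1 − d) × 0.85. The Kaplan-Meier column censors deaths, and the true median comes from the cumulative incidence.

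| d | True by Day 56 | Kaplan-Meier by Day 56 | True median | Kaplan-Meier median | Median shortened by |
|---|---|---|---|---|---|
| 10% | 0.90 × 0.85 = 76.5% | 84% | 36.8 d | 36.0 d | 0.8 d |
| 15% | 0.85 × 0.85 = 72.3% | 83% | 37.5 d | 36.3 d | 1.2 d |
| 25% | 0.75 × 0.85 = 63.8% | 81–82% | 39.5 d | 36.8 d | 2.7 d |

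A second set of assumptions (recovery Normal(36, 8), no permanent non-recovery, constant death hazard giving 5%, 10% or 20% deaths by Day 56) gives 99.4% by Kaplan-Meier against 96.2%, 92.9% and 86.2%. The direction is the same and the size differs.

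**4. Scheduled blood counts**

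The Appendix D hematology row has induction Days 1, 3, 5, 6 (cycle 2 only), 8, 14, 21 and 35, and consolidation Days 1, 3, 6 and 35. The visits headed "6.4.2.3 Cycle 1 Days 14 and 21" list an ECG only. With Day 35 ± 7 meaning Days 28 to 42:
- Induction, after Day 21: 28 − 21 = 7 to 42 − 21 = 21 days without a scheduled CBC.
- Consolidation, after Day 6: 28 − 6 = 22 to 42 − 6 = 36 days.
- None is scheduled at Day 56, the cut-off for delayed recovery in 9.10.

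**The case against.** Several stronger readings are tempting, and the documents do not support them.

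- **That every consolidation cycle scores 0 for both lineages.** Section 5.2 admits CRi patients to consolidation, and Section 9.2 allows CRi with platelets below 100,000/µL, so a patient may enter at or below 50,000. For cycle 2, Section 5.2.3 says only that patients with persistent low counts could skip it, which is not a count requirement. The zero is secure for neutrophils at cycle 1 only.
- **That the protocol censors deaths.** No text says so for this endpoint. Section 10.4.2 names Kaplan-Meier only for DOR, EFS and OS. The accurate statement is that there is no rule, and that the general sentence in 10.4 would lead to censoring by default.
- **That the Kaplan-Meier error is about 11 points.** That is the Day 56 proportion at an assumed 15% deaths. The plan reports a median with its confidence interval and no Day 56 proportion. On the same assumptions the median moves by about 1 to 3 days.
- **That recovery can be dated only to within weeks.** This holds for Appendix D alone. The thrice-weekly labs would date recovery to within 2 to 3 days for discharged induction patients and outpatient consolidation patients. Sparse counts would also make recovery look later, which is the opposite direction to the other defects.
- **That the lead-in stopping rule is compromised.** That rule counts individual patients with delayed recovery beyond 56 days. The Day 1 and Kaplan-Meier defects do not enter it. A transfused count could affect only its platelet limb.

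It is also fair that being listed first among the secondary endpoints implies no hierarchy. What stands is the missing nadir, the missing transfusion condition, the absence of a rule for death, and the mismatch between Appendix D and Section 5.2.1.

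**Conclusion.** The concern holds in this limited form. As worded, Section 9.10 gives a neutrophil recovery time of 0 days at consolidation cycle 1 for any patient whose ANC has not dropped again, and that value is useless for the comparison in Section 1.5. This follows from the text and needs no assumption. Platelet recovery may reflect transfusion, by an amount the documents do not let us estimate, and its threshold is inconsistent.

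The handling of death is undefined. If deaths are censored, the proportion recovered is overstated and the planned median shortened. The 81–84% against 64–77% and the 1 to 3 days rest on assumed death and non-recovery rates. The direction does not depend on those rates.

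The blood-count issue is secondary. The extra labs exist for some patients, but they are not in Appendix D and no text makes them data for this endpoint. Inpatients have no stated frequency beyond the scheduled visits. None of this touches the test of the response rate.

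**What to change.** **Section 9.10.** Define recovery per cycle as the first ANC ≥500/µL after a value below 500 in the same cycle. Define platelet recovery in the same way, at one threshold shared with 2.3.2 and without recent transfusion, with the sponsor stating the interval. Report cycles with no nadir separately, and summarise induction and consolidation separately.

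**Section 10.4.** Estimate the cumulative incidence of recovery, with death and new anti-leukemia therapy as competing events, and take the median from that curve.

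**Appendix D and Section 5.2.1.** Reconcile the two on CBC frequency, including inpatients and the period to Day 56, and state that the thrice-weekly results are entered in the eCRF for this endpoint.

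**Cost.** A few sentences, one schedule row, and some extra data entry and analysis. For patients covered by 5.2.1 the draws already exist; carrying counts to Day 56 for others may need new ones. Recovery figures will look less favourable than under the present wording.

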All grades of gastrointestinal toxicities associated with CPX-351 were similar to standard induction 7+3, with the most frequent being nausea (47%), diarrhea/colitis (45%), mucositis (44%), and constipation (40%). However, Grade 3 and higher gastrointestinal toxicities were less than 10% (Lancet et al 2016b). In Phase I/II investigations, quizartinib was found to be associated with all grades of nausea (16%), vomiting (11%), and diarrhea (18%) (Cortes et al 2013, Schiller et al 2014).

Given that the toxicities identified with each agent have minimal overlap, it is hoped that the novel combination will not result in the potentiation of the toxicity of either agent alone. A potential beneficial effect of this combination may be the protective effect of quizartinib on normal hematopoietic progenitor cells after exposure to chemotherapy. If dosed sequentially following CPX-351, this may attenuate the effects that CPX-351 has on healthy stem cells without compromising the effect on the leukemic cells (Taylor et al 2017). This potential benefit of the novel combination will be measured based on the timing of myeloid count recovery and comparing this data to data from prior CPX-351 studies.

It is assumed that there are four patient groups who may derive benefit on study for relapsed or refractory FLT3 mutation-positive AML. The first group includes patients who have primary refractory FLT3 mutation-positive AML and who fail first-line therapy with routine induction regimens with or without an FLT3 inhibitor. The second group includes patients with FLT3 mutation-positive AML who have relapsed after HCT. In both scenarios, the study intervention will likely act as a bridge to either an HCT or a DLI. The third group includes patients with relapsed FLT3 mutation-positive AML who were excluded from or declined alloHCT. In this patient population, the FLT3 inhibitor would continue as maintenance therapy. The final group of patients includes those who acquire an FLT3 mutation at relapse. This occurs more frequently in patients with epigenetic-modifying gene mutations at diagnosis (IDH1/2, DNMT3A, TET2) (Shih et al 2002, Wakita et al 2013). Depending on the management choice at the initial diagnosis and initial CR, the last clinical scenario may be a bridge to a first or second HCT or to a DLI.

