2.3.2 Secondary Endpoints

- Time to ANC recovery >56 days ($\geq 500/\mu\text{L}$) and platelet count recovery >56 days ($\geq 50,000/\mu\text{L}$)
- Number of patients proceeding to an alloHCT
- Time to PD or DOR
- EFS
- OS

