5.2 Treatment Plan

The plan for administration is divided into three phases: induction, consolidation, and maintenance. In patients who decline HCT or cellular therapy (CT) intervention or are ineligible, the patient would proceed through induction, consolidation, and maintenance.

Patients who achieve a CR (CR or CRi) after induction(s), will proceed to consolidation followed by the maintenance phase. In patients who achieve a PR, re-induction can occur for one additional cycle followed by consolidation and maintenance phases if a CR is achieved with re-induction. In patients who achieve a CR or PR after induction and/or consolidation and an HCT or other CT intervention (e.g., HCT or DLI) is indicated, maintenance therapy would be initiated no earlier than Day 30 after the HCT or CT intervention. If the patient is on quizartinib prior to HCT or CT intervention, quizartinib should be discontinued 7 days prior if a conditioning therapy is utilized. If proceeding to a CT intervention without conditioning therapy (e.g., DLI), quizartinib should be discontinued one day prior to CT intervention.

Response assessment will occur by BM biopsy/aspirate 21 days (± 2 days) from CPX-351 induction and/or re-induction therapy as well as Day 35 (± 7 days) during induction and consolidation therapy (within 4 days after neutrophil as defined as a peripheral ANC $\geq 500/\mu\text{L}$ for 24 hours). In the event of a delayed neutrophil recovery, defined as having a peripheral ANC $< 500/\mu\text{L}$ at Day 42 from the first day of CPX-351 treatment, a BM biopsy will be taken to assess persistent disease. During the maintenance phase, subsequent response assessments by BM biopsy/aspirate will be done on Day 24 (± 3 days) of a 28-day treatment cycle during Cycles 3, 6, 12, and 24.

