10. STATISTICAL CONSIDERATIONS

10.1 Statistical Design

This is a multi-center, open-label, two-part prospective Phase II study of patients with relapsed or refractory FLT3-ITD mutation-positive AML. The study is designed to assess the safety and tolerability as well as the efficacy of administering CPX-351 with quizartinib, a second-generation FLT3 inhibitor.

A response rate (CR + CRi) of $\geq 50\%$ is targeted with 40% or less considered unacceptable. This is assumed to be an acceptable estimate based on CR + CRi/CRp of 48.2% reported with quizartinib monotherapy in a relapsed or refractory patient with FLT3-ITD AML (Cortes et al 2019). Of note, prior FLT3-targeting inhibitor exposure is permitted on this study. However, patients receiving a prior FLT3-targeting inhibitor were excluded in the QUANTUM-R study. Expected CR+CRi in relapsed or refractory patients receiving standard intensive or non-intensive salvage chemotherapy harboring an FLT3 mutation is 27% (Cortes et al 2019). The estimated response in those with relapsed/refractory FLT3-ITD AML receiving CPX-351 alone cannot be estimated. However, in a poor-risk EPI patient population, CR+CRi was reported as 39.3% (Cortes et al 2015). However, FLT3-ITD mutation presence was not utilized in the generation of EPI prognostication, and those with an FLT3-ITD mutation could in fact have a reduced response within all EPI risk groups. Thus, the expected response must be based upon the QUANTUM-R study of those receiving standard salvage options harboring an FLT3-ITD mutation.

In the safety lead-in, 10 patients will be enrolled to receive CPX-351 with quizartinib. If > 3 patients experience delayed neutrophil count recovery > 56 days or delayed thrombocytopenia recovery > 56 days from the first day on the study regimen, or if > 3 patients develop a non-hematologic toxicity, defined as a Grade 4 non-hematologic AE determined to be probably related to the combined treatment or a Grade 4 neutropenia, then the study will be terminated.

Assuming safety parameters are met, the first 10 patients will be followed for response in Part 2 of the study.

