10.5 Analysis Time Points

10.5.1 Safety Review

The safety lead-in consists of the first 10 patients enrolled. If >3 patients experience delayed neutrophil count recovery >56 days from the first day receiving the study regimen, defined as having a peripheral blood ANC <500/ μ L without evidence of residual disease by BM biopsy, or if >3 patients develop a non-hematologic toxicity, defined as a Grade 4 non-hematologic AE determined to be probably related to the combined treatment, then the study will be terminated.

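### Section 9.10 defines count recovery by counts alone, so in induction it does not separate cytopenia with residual leukemia from myelosuppression, as 10.5.1 does for neutrophils

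*Combined protocol and SAP*

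**What the plan says.** Section 9.10 starts the clock at each CPX-351 cycle and stops it when the count passes a threshold (ANC 500/µL, platelets 50,000/µL). Its two delay definitions open "Delayed neutrophil recovery is defined as having an ANC" and "Delayed platelet recovery is defined as having a platelet count". Each is completed by a count threshold and more than 56 days, with no marrow condition. Section 2.3.2 lists the endpoint as "Time to ANC recovery >56 days", with the platelet counterpart and again no marrow condition.

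Section 10.5.1, the lead-in safety review, uses the same ANC threshold and the same 56 days but counts a patient only "without evidence of residual disease by BM biopsy". It has no platelet criterion. The synopsis, Section 5 and Section 10.1 state the lead-in rule with platelets and without the marrow condition.

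Section 1.5 says that the possible protective effect of quizartinib on normal marrow "will be measured based on the timing of myeloid count recovery and comparing this data to data from prior CPX-351 studies". For an ANC still below 500/µL at Day 42, Section 5.2 says "a BM biopsy will be taken to assess persistent disease".

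Sections 9.5, 9.7 and 9.9 give censoring rules for DOR, EFS and OS. Section 9.10 gives none. Section 10.4 applies Kaplan-Meier to time-to-event endpoints in general, and 10.4.2 names only ORR, DOR, EFS and OS.

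**The concern.** Low counts after induction can come from the drugs or from leukemia still occupying the marrow. A definition without a marrow condition takes in both. A patient with an ANC below 500/µL past Day 56 and leukemia on biopsy is delayed under 9.10 and not delayed under 10.5.1.

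Time to count recovery is the first secondary objective, and Section 1.5 gives it an interpretive job: to show whether the combination spares normal marrow relative to earlier CPX-351 studies. If the result shifts with the proportion of patients who respond, a difference from those studies cannot be read as an effect on normal marrow. The missing rules for death, new therapy and transplant before recovery add to this, because each removes patients from observation in a way related to response.

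**Working it through.** **Design figures that supply the response rates (Section 10.2).** With 30 evaluable patients and rejection at 13 or more responses, the exact one-sided error at 27% is 0.0395 and the power at 50% is 0.819. A cut-off of 12 would give an error of 0.084. Allowing 10% non-evaluable, 30 / 0.90 = 33.3, rounded up to 34. The plan's figures are reproduced. Non-response is then 1 − 0.50 = 50% at the target and 1 − 0.27 = 73% at the null. The null rate is a rejection boundary, not a forecast.

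**Inputs for the endpoint.** The plan gives no figure for delayed recovery under its own definition, so this is a scenario calculation for an induction cycle.
- r: response rate, 0.50 or 0.27 (Section 10.2). CR/CRi stands for a clear marrow.
- m: delay rate in responders. Assumed to be 0.17, the share in Section 7.5.2 with ANC below 500 beyond Day 42 of CPX-351 induction. The documents give no Day 56 rate, and 7.5.2 does not say that the 17% is limited to clear marrows.
- f: share of non-responders still observed and cytopenic past Day 56. Not in the documents, so it is varied.

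Delayed recovery as a share of all patients = r·m + (1 − r)·f. With the 10.5.1 exclusion only r·m remains.

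| f | r = 0.50 | r = 0.27 |
|---|---|---|
| 0 (same as applying the exclusion) | 8.5% | 4.6% |
| 0.2 | 18.5% | 19.2% |
| 0.5 | 33.5% | 41.1% |

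Example: 0.50 × 0.17 + 0.50 × 0.2 = 0.085 + 0.100 = 0.185.

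**Movement with response.** Holding m fixed and lowering r from 0.50 to 0.27 changes the rate by 0.23 × (f − 0.17). That is +7.6 percentage points at f = 0.5, +0.7 at f = 0.2 and −3.9 at f = 0. The endpoint shifts with no change in the assumed responder delay rate, and the direction depends on f.

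**Sensitivity at r = 0.50.** For f = 0, 0.2 and 0.5, m = 10% gives 5%, 15% and 30%. For platelets, the Day 42 rate of 28% in 7.5.2 gives 14%, 24% and 39%.

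**Lead-in rule, neutrophil criterion only.** The chance of more than 3 of 10 patients is P(X ≥ 4) for a binomial with n = 10. At r = 0.50 and m = 0.17 it is 0.7% with the exclusion (p = 0.085). Without it, the chance is 9.6% at f = 0.2 (p = 0.185) and 44.5% at f = 0.5 (p = 0.335).

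**The case against.** The best defence is that 9.10 is a descriptive endpoint and 10.5.1 a stopping rule for ten patients. The two may differ on purpose, and 9.10 is silent on leukemia rather than saying that leukemic cytopenia counts. The difference in purpose is fair. Silence does not help, because a definition without an exclusion counts everyone who meets it, and 10.5.1 shows that the distinction was recognised.

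Several features also keep f down. Section 5 follows non-responders only until new therapy starts, 6.4.5 ends the study at progression, and 6.4.6 schedules no blood counts. Patients in PR may be re-induced after the Day 35 (±7) marrow, and 9.10 restarts the clock with each cycle. Consolidation cycles, also covered by 9.10, go to patients in remission. These points stand, and they confine the problem to induction and re-induction.

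A reader might infer that the endpoint mostly measures non-response. The documents do not support that. At an ORR of 50%, non-responders make up the majority of delayed cases only if f exceeds 0.50 × 0.17 / 0.50 = 0.17 for neutrophils, or 0.28 for platelets. At 27% the break-evens are 0.063 and 0.104. None can be checked without f. Nor is every delay in a non-responder leukemic, since these patients received the same drugs. At f = 0.5 and ORR 50%, non-responders make up 0.25 / 0.335 = 75% of delayed cases. If 17% of them would have been delayed by the drugs anyway, the leukemic excess is 0.50 × (0.5 − 0.17) / 0.335 = 49%.

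Finally, the 10.5.1 condition covers neutrophils only, so carrying it to platelets is an extension. Making the marrow-clear patients the only main summary would select on a post-treatment result, and the documents do not say whether the earlier CPX-351 recovery figures were restricted in that way.

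**Conclusion.** The point holds in a limited form. In induction and re-induction cycles, 9.10 does not separate cytopenia with residual leukemia from myelosuppression, and the plan has no rule for events that precede recovery. The comparison in Section 1.5 is therefore confounded with response.

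The size is uncertain. At an ORR of 50%, delayed neutrophil recovery runs from 8.5% to 33.5% of all patients as f goes from 0 to 0.5. This rests on an assumed f and on a Day 42 rate, from CPX-351 without quizartinib, standing in for Day 56 in responders. No claim about the majority cause of delay is warranted.

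Separately, the lead-in stopping rule is stated in two incompatible ways, and the same ten patients could meet one and not the other.

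**What to change.** In 9.10 and 10.4:
- Report time to recovery and delayed recovery, for neutrophils and platelets, by marrow status of the cycle (no residual leukemia versus residual leukemia). Take the status from the recovery marrow or the Day 42 marrow, and keep the all-patient result alongside.
- State in advance whether new anti-leukemic therapy, start of transplant conditioning, a new CPX-351 cycle and death before recovery are competing events or censoring. For death, a competing-event analysis is the more natural choice, because censoring treats the patient as still able to recover.
- Show consolidation cycles separately.

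The sponsor must also reconcile the lead-in stopping rule across 10.5.1, the synopsis, Section 5 and 10.1, on both the residual-disease exclusion and platelets.

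The cost is wording and extra tables, since Section 5.2 already provides for most of the marrow data. The Day 42 marrow is triggered by ANC alone and precedes the Day 56 cut-off by two weeks, so some cycles, particularly those with low platelets only, will depend on the recovery marrow. The subgroups are small: about 8 (0.27 × 30) to 15 (0.50 × 30) of 30 patients with a clear marrow. Intervals will be wide, and the split is conditional on a result observed after treatment, so it should be described as such.
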